2.4.3.1 Clinical pharmacokinetics

Final PK data of the first phase 1 study conducted with monalizumab in RA and preliminary PK data from the IND.221 trial (part 1) in gynecological malignancies are presented in the Investigator Brochure.

The pharmacokinetics of monalizumab was originally evaluated in a first phase 1 study conducted in RA. The PK of monalizumab was as expected for a monoclonal antibody that binds to a membrane-bound target, which expression is restricted to a small subset of immune cells, and which Ab does not demonstrate intracellular internalization.

The PK of monalizumab was similar in RA patients and gynecologic cancer patients (IND.221 part 1 study). In patients with gynecologic malignancies (ovarian, endometrial and cervical cancer), the PK of monalizumab was dose proportional across the entire dose range (1-10 mg/kg). There was a 1.4-2 fold accumulation of monalizumab after the administration of four intravenous doses, which was consistent with administration frequency and the half-life of 2-3 weeks seen with single dose i.v. dosing in RA patients at similar doses.

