7.4.1 Time Period for Collection of Adverse Events

Adverse events will be collected from time of signature of informed consent, enrollment, randomization, throughout the treatment period and including the follow-up period of 90 days after the last dose of Durvalumab post-operatively. Serious adverse events will be recorded from the time of informed consent signature through 90 days after the last dose of Durvalumab.

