- Unless otherwise noted, the electronic SAE application (eSAE) will be utilized for safety reporting to the IND Office and MDACC IRB.
- Serious adverse events will be captured from the time of the first protocol-specific intervention, until 90 days after the last dose of drug, unless the participant withdraws consent. Serious adverse events must be followed until clinical recovery is complete and laboratory tests have returned to baseline, progression of the event has stabilized, or there has been acceptable resolution of the event.
- Additionally, any serious adverse events that occur after the 90 day time period that are related to the study treatment must be reported to the IND Office. This may include the development of a secondary malignancy.

Reporting to FDA:

- Serious adverse events will be forwarded to FDA by the IND Sponsor (Safety Project Manager IND Office) according to 21 CFR 312.32.

It is the responsibility of the PI to ensure serious adverse events are reported according to the Code of Federal Regulations, Good Clinical Practices, the protocol guidelines, the IND Office guidelines, and Institutional Review Board policy.

Attribution	Grade 1	Grade 2	Grade 3	Grade 4	Grade 5
Unrelated	Phase I	Phase I	Phase I Phase II	Phase I Phase II Phase III	Phase I Phase II Phase III
Unlikely	Phase I	Phase I	Phase I Phase II	Phase I Phase II Phase III	Phase I Phase II Phase III

Possible	Phase I Phase II	Phase I Phase II Phase III	Phase I Phase II Phase III	Phase I Phase II Phase III
Probable	Phase I Phase II	Phase I Phase II Phase III	Phase I Phase II Phase III	Phase I Phase II Phase III
Definitive	Phase I Phase II	Phase I Phase II Phase III	Phase I Phase II Phase III	Phase I Phase II Phase III

7.5.1 **Reporting of Serious Adverse Events**

All SAEs will be reported, whether or not considered causally related to the investigational product, or to the study procedure(s). The reporting period for SAEs is the period immediately following the first protocol intervention through 90 days after the last dose of durvalumab or until the initiation of alternative anticancer therapy. The investigator is responsible for informing the Ethics Committee and/or the Regulatory Authority of the SAE as per local requirements.

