7.6.1.2 Death

All deaths that occur during the study, or within the protocol-defined 90-day post-last dose of durvalumab + tremelimumab safety follow-up period must be reported to AstraZeneca as follows:

- Death that is clearly the result of disease progression should be documented but should not be reported as an SAE.
- Where death is not due (or not clearly due) to progression of the disease under study, the AE causing the death must be reported to AstraZeneca as a SAE within **24 hours**. The report should contain a comment regarding the co-involvement of progression of disease, if appropriate, and should assign main and contributory causes of death.
- Deaths with an unknown cause should always be reported as a SAE.

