Laboratory	X	X	X	X	X	X	CBC w/differential and platelet count, LFTs (ALT, AST, total bilirubin, alkaline phosphatase), BUN or serum urea level, creatinine, Ca, Mg, Na, K, Cl, glucose)
CEA	X			X		X	
TSH/FT4	X			X			
Lipase/amylase	X						
Immunogenicity Assessments, Peripheral Blood	X				X	X (at first visit only)	

Pregnancy test (WOCBP only)		X	As indicated clinically						Serum or urine pregnancy test to be done within 72 hours of dose				
ECOG PS	X	X	X	X	X			see appendix 1					
Adverse Events Assessment	X	X	X	X	X			Per CTCAE v4.03 for Cohort A and v5.0 for Cohorts B and C					
CT C/A/P with IV contrast with tumor measurements					X	X							
Immunogenicity Assessments, Peripheral Blood	Up to 12 tubes of blood with 5ml each will be collected for immunological assessment. For specific details see laboratory manual (up to 4 missed blood draws are allowed)												
	
CEA: Carcioembryonic Antigen; ECOG PS: Eastern Cooperative Oncology Group Performance Status; TSH: Thyroid stimulating hormone; FT4: Free T4; WOCBP: Women of child bearing potential; CT C/A/P: CT scan chest, abdomen and pelvis
 
Toxicity 30 day f/u can happen 30 days (+/- 2 weeks) after last treatment dose and this can be done by phone call.
 
Note after one year of follow-up without recurrence schedule of follow-ups can be adjusted according to standard of care. This will take precedence over the study calendar.
												

Table 10.3 Post-Resection Study Calender for Cohorts (B and C)

TIME PERIOD	Post-operative evaluation	Wk	Wk	Comment							
	1 (same day as Durvalumab)	3	5	7	9	11	13	15	every 4 months		
	(0.5-2wks post surgery)	+/-3d	+/-6 weeks								
PROCEDURE											
Durvalumab		X		X		X		X			
Oleclumab (cohort B)		X	X	X	X	X	X	X			If patient requires >12 weeks for postop recovery, they will not be initiated on adjuvant immunotherapy
Monalizumab (cohort C)		X		X		X		X			
Clinic Visit		X	X	X	X	X	X	X	X		
Physical Examination		X	X	X	X	X	X	X	X		
Vital Signs		X	X	X	X	X	X	X	X		Including BP, HR,

										temperature
Review of Concomitant Medication		X	X	X	X	X	X	X	X	
Laboratory		X	X	X	X	X	X	X	X	CBC w/differential and platelet count, LFTs (ALT, AST, total bilirubin, alkaline phosphatase), BUN or serum urea level, creatinine, Ca, Mg, Na, K, Cl, glucose)
CEA	X								X	X
TSH/FT4	X			X		X		X		
Lipase/amylase	X									
Immunogenicity Assessments, Peripheral Blood	X			X				X		X (at first visit only)

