Pregnancy test (WOCBP only)		X	As indicated clinically							Serum or urine pregnancy test to be done within 72 hours of dose
CT C/A/P with IV contrast with tumor measurements								X		X
ECOG PS		X		X		X		X		see appendix 1
Adverse Events Assessment		X	X	X	X	X	X	X		Per CTCAE v4.03 for Cohort A and v5.0 for Cohorts B and C
Immunogenicity Assessments, Peripheral Blood	Up to 12 tubes of blood with 5ml each will be collected for immunological assessment. For specific details see laboratory manual (up to 4 missed blood draws are allowed)									

	
CEA: Carcinoembryonic Antigen; ECOG PS: Eastern Cooperative Oncology Group Performance Status; TSH: Thyroid stimulating hormone; FT4: Free T4; WOCBP: Women of child bearing potential; CT C/A/P: CT scan chest, abdomen and pelvis
 
Toxicity 30 day f/u can happen 30 days (+/- 2 weeks) after last treatment dose and this can be done by phone call.
 
Note after one year of follow-up without recurrence schedule of follow-ups can be adjusted according to standard of care. This will take precedence over the study calendar.

--	--

Table 10.4 Collection Times for Vitals During Treatment Period

Treatment Arm	Durvalumab			Tremelimumab			Oleclumab			Monolizumab		
	Pre-dose	During	EOI	Pre-dose	During	EOI	Pre-dose	During	EOI	Pre-dose	During	EOI
Cohort A	Within 30 mins	N/A	Within 15 mins	Within 30 mins	Q15 mins	Within 5, 30 and 60 mins	N/A	N/A	N/A	N/A	N/A	N/A
Cohort B	Within 30 mins	N/A	Within 15 mins	N/A	N/A	N/A	Within 30 mins	None	Within 15 mins	N/A	N/A	N/A
Cohort C	Within 30 mins	N/A	Within 15 mins	N/A	N/A	N/A	N/A	N/A	N/A	Within 30 mins	N/A	Within 5, and 30

All Cohorts will require an additional 2-hour observation period for **Dose-1** of each drug. This will not be required for subsequent doses unless the subject experiences an infusion reaction. Note: exact times for vital signs are approximate.

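### Adverse events are to be collected to 90 days after the last dose, but no assessment is scheduled after the 30-day call, so more than half of that period is uncovered

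*Combined protocol and SAP*

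**What the plan says.** Section 7.4.1 collects AEs from consent "throughout the treatment period and including the follow-up period of 90 days after the last dose of Durvalumab post-operatively". For SAEs it adds: "Serious adverse events will be recorded from the time of informed consent signature through 90 days after the last dose of Durvalumab". Section 7.5 captures SAEs "until 90 days after the last dose of drug, unless the participant withdraws consent", and Section 7.6.1.2 refers to a "protocol-defined 90-day post-last dose of durvalumab + tremelimumab safety follow-up period". Section 7.5.1 also gives 90 days for SAE reporting, but lets it end sooner if the patient starts another anticancer treatment.

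The calendars in Section 10 give the visits:

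- **Table 10.1 (enrolment to resection):** AE assessment at screening and at the pre-resection visit, 3 to 10 weeks after the neoadjuvant dose. There is no 30-day footnote.
- **Table 10.2 (Cohort A, after resection):** AE assessment at the post-operative evaluation and at weeks 1, 5, 9 and 13. The 4-monthly column has no AE mark.
- **Table 10.3 (Cohorts B and C, after resection):** AE assessment during adjuvant treatment, with no mark in the 4-monthly column.
- **Footnote to Tables 10.2 and 10.3:** "Toxicity 30 day f/u can happen 30 days (+/- 2 weeks) after last treatment dose and this can be done by phone call".

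Safety is a primary endpoint (Section 13.1). Its planned analysis is a tabulation of AEs (Section 13.4). Neither section gives a time limit.

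**The concern.** The protocol sets a 90-day duty to collect AEs, but a site that follows the calendar has its last planned safety contact at about day 30. What happens between that contact and day 90 is recorded only if it comes to light some other way. Serious events and deaths have their own reporting routes. A non-serious late event, such as a rash or a mild endocrine or laboratory abnormality, is the kind most easily missed.

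At stake is how complete the AE tabulation is for a primary endpoint. A reader who sees a 90-day collection period in the methods will take the table to be equally well ascertained over all 90 days.

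A second difficulty concerns treated patients who receive no adjuvant immunotherapy. Section 5.1 allows post-operative chemotherapy instead, and Section 2.6 reports that 3 of the first 14 patients to reach the point of surgery were not resected. Section 7.4.1 dates the end of AE collection from a post-operative durvalumab dose that these patients never receive.

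**Working it through.** The plan states no coverage figure to reproduce, so this is calendar arithmetic.

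**Inputs.** Collection period of 90 days after the last dose (Section 7.4.1). Last scheduled safety contact on day 30, plus or minus 14 days, so day 16 to day 44 (footnotes to Tables 10.2 and 10.3). Neoadjuvant dose to resection 21 to 70 days, and resection to adjuvant start 28 to 84 days (Section 5.1). Durvalumab from week 1 to week 13, (13 − 1) × 7 = 84 days. Screening 0 to 14 days.

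**1. Days after the last scheduled contact.** Gap = 90 − contact day; share = gap / 90.

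| Contact day | Gap (days) | Share of 90 |
|---|---|---|
| 16 | 74 | 82% |
| 30 | 60 | 67% |
| 44 | 46 | 51% |

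The gap exceeds half under every permitted timing.

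**2. Whether the 4-monthly visit closes it.** Its starting point is not stated, so I tried three. Four months is 4 × 30.4375 ≈ 122 days, with a window of 42 days either side. Days are counted from the last durvalumab dose at week 13.

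- From week 13: day 122 (80 to 164).
- From week 1: 122 − 84 = day 38 (−4 to 80).
- From surgery, with adjuvant start at 4 weeks: first visit at day 10 (−32 to 52), second at day 132 (90 to 174). With adjuvant start at 12 weeks: second visit at day 76 (34 to 118).

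A visit may fall inside the 90 days, but this is not assured, and no AE assessment is marked for it.

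**3. The gap against the whole AE period.** The whole period is screening + time to surgery + time to adjuvant start + adjuvant treatment + 90.

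- Shortest: 0 + 21 + 28 + 84 + 90 = 223 days.
- Longest: 14 + 70 + 84 + 84 + 90 = 342 days.
- With a day-30 call: 60/342 = 18% to 60/223 = 27%.
- Over the whole allowance: 46/342 = 13% to 74/223 = 33%.

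**4. Overlap with the stopping rules.** The TOX window ends at surgery, or 4 weeks after the first durvalumab dose if surgery does not take place as scheduled (Section 13.3.2). The TOXpost window ends at the final adjuvant dose, up to 12 weeks (Section 13.3.3). For patients given adjuvant immunotherapy, the gap lies wholly after both, so the overlap is zero.

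**5. Patients without adjuvant immunotherapy.** Assume that the 90 days run from the neoadjuvant dose; the protocol does not say. Leave the 30-day call aside, since Table 10.1 does not carry it.

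- Resected, Cohort A: the post-operative mark is 3.5 to 14 days after surgery, so day 21 + 3.5 ≈ 25 to day 70 + 14 = 84. That leaves 65 to 6 days.
- Not resected: the last mark is the pre-resection visit, day 21 to 70, if it takes place. That leaves 69 to 20 days.

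Coverage in this group varies widely, and the 67% in step 1 should not be carried over to it.

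**The case against.** The best defence is that Section 7.4.1 governs and the calendar need not repeat it. The duty to collect to day 90 stands without a mark in a table. SAE capture and death reporting run to day 90 as well. Patients removed for unacceptable AEs are followed until the event resolves or stabilises (Section 5.4, Duration of Follow Up). Cohort A's 4-monthly visits include a clinic visit, examination, vital signs and laboratory tests, which could bring events to light. All of this stands. It limits the likely loss mainly to non-serious events, and it rules out saying that late events are found only if patients volunteer them. It does not supply a scheduled assessment.

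A reader might infer that most of the primary safety window is unobserved. The documents do not support that: they define no such window, and the gap is 13% to 33% of the whole AE period. Nor is safety monitoring weakened, because both stopping rules end earlier.

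A reader might also point to residual antibody at day 30. Section 2.4.3.1 refers, for monalizumab, to "the half-life of 2-3 weeks seen with single dose i.v. dosing", which gives 0.5^(30/14) = 23% to 0.5^(30/21) = 37% remaining. The 22.1-day half-life for tremelimumab in Section 2.3.3 gives 0.5^(30/22.1) = 39%. These are exposure figures, not event rates. The documents give no onset times for late immune-mediated events and no durvalumab half-life, so the number of missed events cannot be estimated.

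Finally, the columns of Table 10.3 are not cleanly aligned in the text available to me. I rely only on the absence of an AE mark in its 4-monthly column, not on the exact last marked week.

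**Conclusion.** The mismatch is real but modest. After adjuvant treatment, 60 of the 90 post-dose collection days have no scheduled AE assessment if the call is on day 30, with a range of 46 to 74 days. This takes the calendars as written and counts a 4-monthly visit as an AE assessment only where it is marked as one. The consequence is possible under-counting of late, mainly non-serious, AEs in the tabulation. The size of that under-count is unknown. The TOX and TOXpost boundaries and their operating characteristics are not affected.

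For treated patients who go to chemotherapy or are not resected, the problem is different: the collection period is not clearly defined. Section 7.4.1 dates AE collection from a dose they do not receive, Table 10.1 lacks the 30-day footnote, and Section 7.5.1 may end SAE reporting when chemotherapy starts.

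**What to change.** - Add to Tables 10.1, 10.2 and 10.3 one AE/SAE contact, phone allowed, at 90 days after the last dose of any study antibody, for every treated patient. Keep the 30-day call.
- Mark AE assessment at any 4-monthly visit that falls inside the 90 days.
- Reconcile Sections 7.4.1 and 7.5.1 with this. Section 7.4.1 should cover patients with no post-operative durvalumab. Section 7.5.1 should say whether collection continues after another anticancer treatment starts. The period for patients who go to chemotherapy or are not resected would then be explicit.

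A contact at day 90 reduces the uncovered part of the period from 46–74 days to zero. The cost is at most about 25 + 15 + 15 = 55 phone calls and a calendar edit. AE collection becomes slightly longer for patients who start chemotherapy. Treatment, sample size and stopping rules do not change.

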11. MEASUREMENT OF EFFECT

RECIST 1.1 will be used to identify measurable disease on baseline CT scans. Tumor measurements will be made upon restaging CT scans prior to surgery. Further imaging will be performed according to the study outline in section 5 and study calendar in section 10. No tumor measurements will take place post-operatively as the goal of therapy is no evidence of disease. Suspected first site of recurrence should be biopsied to confirm CRC recurrence unless interval imaging demonstrates clear growth / progression.

11.1.1. Definitions

Evaluable for toxicity. All patients will be evaluable for toxicity from the time of enrollment.

Evaluable for recurrence. Only those patients who have measurable disease present at baseline, have received at least one cycle of therapy, and have had their disease re-evaluated will be considered evaluable for recurrence. These patients will have their response classified according to the definitions stated below.

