1.2. Secondary Objectives

1. Explore the changes in various immune parameters, including PD-L1 and PD-1 expression in the tumor, over treatment and correlate with response and survival with goal of biomarker discovery.
2. Estimate the relapse-free survival (RFS) in all enrolled subjects.

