3. PATIENT SELECTION

3.1 Eligibility Criteria

- 3.1.1 Patients must have histologically or cytologically confirmed colorectal cancer with liver or lung metastases deemed resectable by a liver or thoracic surgeon, respectively (resectability may involve the use of ablative techniques to some but not all liver or lung metastases). Patients with a primary colorectal tumor that is planned for surgical resection are eligible. In addition patients with nonspecific lung lesions (lesions that are uncertain to be metastases given their small size, defined here as <1cm) are eligible.
- 3.1.2 Patients must have measurable disease, defined as at least one lesion that can be accurately measured in at least one dimension (longest diameter to be recorded) as ≥ 10 mm with spiral CT scan. See Section 11 for the evaluation of measurable disease.

- 3.1.3 All lines of prior therapy accepted. Subjects with prior hepatic or extra-hepatic resections of metastatic disease will be included.
- 3.1.4 Age ≥ 18 years. Because no dosing or adverse event data are currently available on the use of tremelimumab, oleclumab, or monalizumab in combination with durvalumab in patients <18 years of age, children are excluded from this study.
- 3.1.5 Life expectancy of greater than 6 months.
- 3.1.6 ECOG performance status ≤ 1 (Karnofsky $\geq 70\%$; see Appendix1).
- 3.1.7 Patients must have normal organ and marrow function as defined below:

- leukocytes	$\geq 3,000/\text{mcL}$
- absolute neutrophil count	$\geq 1,500/\text{mcL}$
- platelets	$\geq 100,000/\text{mcL}$
- total bilirubin	$< 1.5 \times$ institutional normal limits (subjects with known Gilbert syndrome are eligible with total bilirubin $< 3.0 \text{ mg/dL}$)
- Hemoglobin	$\geq 9\text{g/dL}$
- AST(SGOT)/ALT(SGPT)	$\leq 3 \times$ institutional upper limit of normal within normal institutional limits
- creatinine	
OR	
- creatinine clearance	$\geq 60 \text{ mL/min}/1.73 \text{ m}^2$ for patients with creatinine levels above institutional normal
- 3.1.8 Known or ordered molecular testing for MSI, BRAF, and KRAS status.

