11.1.4 Response Criteria

Subjects will be monitored for recurrence, not response, and thus no formal response criteria will be employed.

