11.1.5 Relapse-Free Survival

Relapse-Free Survival is defined as the time from surgical excision of CRCLM to evidence of definite recurrence, as determined by the treating physician.

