13. STATISTICAL CONSIDERATIONS

13.1 Endpoints

1. Primary Endpoints

- Feasibility will be assessed by whether or not the patient successfully goes to surgery following the planned treatments, scans, and biopsy.
- Safety will be assessed by CTCAE version 4.03 for cohort A and 5.0 for cohorts B and C.

2. Secondary Endpoints

- Various immune parameters
- Response - irRECIST
- Overall survival (OS) measured from the date of study entry until death from any cause
- Relapse-free survival (RFS) from the date of study entry until relapse or death from any cause

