13.4 Analysis Plan

Primary endpoint: Each combination regimen will be considered feasible if at least 80% of patients successfully undergo surgery. It will be infeasible if fewer than 60% of patients can undergo surgery. If the successful surgery rate is between 60% and 80%, then consideration will be given to toxicity, clinical outcome measures, and immune changes to determine whether this regimen warrants further investigation. The 95% posterior credible interval will be calculated for proportion of patients undergoing surgery. Adverse events will be tabulated.

Additional analyses: Demographic and patient baseline disease characteristics will be summarized for all patients. Descriptive tables and figures will be presented for immune markers. Overall (OS) and relapse-free survival (RFS) will be calculated and plotted by Kaplan-Meier methods[69]. Relationships between baseline characteristics, immune markers, and outcomes (response, OS, or RFS) will be explored with logistic or Cox[70] models as patient numbers allow. No formal hypotheses will be tested, but results will be used to design the next formal trial if toxicity and feasibility are reasonable for further investigation.

The Investigator is responsible for completing a futility/toxicity summary report, and submitting it to the IND Office Medical Affairs and Safety Group, for review and approval. This should be submitted after the first 3 evaluable patients per cohort, have surgery or 4 weeks after the first dose of immune-therapy, whichever comes first, and

every 2 to 4 evaluable patients thereafter, according to the schedule described in the toxicity/futility monitoring tables.

On every summary submission, futility information about previous reported patients will need to be updated to week eight.

A copy of the cohort summary should be placed in the Investigator's Regulatory Binder under "sponsor correspondence".

REFERENCES

1. Siegel, R., et al., *Cancer statistics, 2014*. CA Cancer J Clin, 2014. **64**(1): p. 9-29.
2. Scheele, J., et al., *Resection of colorectal liver metastases*. World J Surg, 1995. **19**(1): p. 59-71.
3. Adam, R. and E. Vinet, *Regional treatment of metastasis: surgery of colorectal liver metastases*. Ann Oncol, 2004. **15 Suppl 4**: p. iv103-6.
4. Parkin, D.M., et al., *Global cancer statistics, 2002*. CA Cancer J Clin, 2005. **55**(2): p. 74-108.

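### The recurrence-evaluability rule in section 11.1.1 conflicts with RFS in all enrolled subjects and, if applied to RFS, would drop deaths before re-evaluation and inflate the estimate

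*Combined protocol and SAP*

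**What the plan says.** Four places in the combined protocol and SAP bear on who enters the RFS analysis and what counts as an event.

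- Section 1.2, secondary objective 2: "Estimate the relapse-free survival (RFS) in all enrolled subjects".
- Section 13.1, secondary endpoints: "Relapse-free survival (RFS) from the date of study entry until relapse or death from any cause".
- Section 11.1.1: only patients with measurable disease at baseline who "have received at least one cycle of therapy, and have had their disease re-evaluated will be considered evaluable for recurrence". The same section makes every patient evaluable for toxicity from enrolment.
- Section 11.1.5: RFS is the "time from surgical excision of CRCLM to evidence of definite recurrence, as determined by the treating physician". Death is not mentioned.

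Section 13.4 says that "relapse-free survival (RFS) will be calculated and plotted by Kaplan-Meier methods". It specifies all patients for the demographic and baseline summaries, but gives no analysis set for RFS and does not refer to 11.1.1.

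**The concern.** Being re-evaluated happens after treatment starts, so the 11.1.1 rule selects patients on a post-treatment outcome. A patient who dies before re-evaluation is an RFS event under 13.1 but not evaluable under 11.1.1. If an analyst takes 11.1.1 as the RFS set, the curve is conditional on surviving to re-evaluation, and the patients lost are the earliest failures.

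Section 11.1.5 narrows the population differently. With the clock starting at surgery, a patient who is never resected has no time origin and drops out, although objective 1.2 includes that patient.

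Section 13.4 says that the results will inform the next trial if toxicity and feasibility are acceptable. An RFS estimate from a favourably selected subset would be an optimistic planning input.

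**Working it through.** The documents state no RFS rate, event count or precision target, so there is no planned figure to reproduce. The sizes below are illustrations.

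**Inputs**
- n = 25 for Cohort A and n = 15 each for Cohorts B and C (sections 5.1 and 13.2).
- Assumed true RFS of 36.2%, with 28.1% and 50% as a range. The first two are 3-year PFS rates from a randomised trial cited in section 2.1.1; 50% is a round assumption.
- Number k of deaths before re-evaluation: assumed to be 0 to 3. The documents give none.
- Unresected fraction: 20%, from the 80% surgery rate assumed in section 13.2, or 3/14, from section 2.6.

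**1. Effect of dropping early deaths.** If the k deaths come before any censoring, S_all(t) = (1 - k/n) × S_evaluable(t), so S_evaluable(t) = S_all(t)/(1 - k/n). From 36.2%:

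| k | n = 25 | n = 15 |
|---|---|---|
| 0 | 36.2% (0) | 36.2% (0) |
| 1 | 0.362/0.960 = 37.7% (+1.5) | 0.362/0.933 = 38.8% (+2.6) |
| 2 | 0.362/0.920 = 39.3% (+3.1) | 0.362/0.867 = 41.8% (+5.6) |
| 3 | 0.362/0.880 = 41.1% (+4.9) | 0.362/0.800 = 45.2% (+9.0) |

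With an assumed 28.1% or 50%, one death adds 1.2 or 2.1 points at n = 25, and 2.0 or 3.6 points at n = 15.

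**2. Effect of dropping early withdrawals.** These patients enter Kaplan-Meier as early censorings and contribute almost nothing to later RFS. A simulation (20,000 runs per setting) used n = 15 and 25, 4% early death, 8% early non-informative withdrawal, re-evaluation at 1, 2.5 or 6 months, an exponential hazard giving 36.2% at 3 years, and RFS read at 24 months. Mean estimates were:
- all patients: 0.487 to 0.488 (check: 0.362^(24/36) × 0.96 = 0.508 × 0.96 = 0.488);
- withdrawals removed: 0.483 to 0.486, so no upward shift;
- deaths and withdrawals removed: 0.504 to 0.507, about 2 points higher, due to the deaths.

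**3. Effect of the origin in 11.1.5.** If all unresected patients were counted as events, S_all = (1 - p) × S_resected. With p = 0.20, 0.80 × 36.2% = 29.0%, which is 7.2 points lower. With p = 3/14, (11/14) × 36.2% = 28.4%. Counting every unresected patient as an event is the extreme choice; the gap shows how much depends on a rule that the plan does not state.

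**4. How long patients are exposed to the exclusion.** Section 11 says "Tumor measurements will be made upon restaging CT scans prior to surgery", and Table 10.1 places a CT before resection. If that scan counts as re-evaluation, only deaths between first dose and that CT are lost. Section 11.1.1 does not say which scan counts. If a postoperative scan is meant, Tables 10.2 and 10.3 schedule the first at week 13 of adjuvant therapy, 12 weeks after it starts. Section 5.1 starts that therapy 4 to 12 weeks after surgery, so the scan falls about 16 to 24 weeks after resection.

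**The case against.** A reader might infer that the plan does remove early deaths from RFS. The documents do not say so. Section 13.4 never ties RFS to the 11.1.1 set, and objective 1.2 names the population outright. Section 11.1.1 goes on to say that these patients' response will be classified, while section 11.1.4 says "Subjects will be monitored for recurrence, not response, and thus no formal response criteria will be employed". The rule may therefore be leftover response wording that was never meant to govern RFS. This stands as a limit on the claim: the exclusion is conditional. It does not remove the conflict, because the rule is labelled as one about recurrence, and recurrence is part of the RFS event.

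A reader might also infer that excluding early withdrawals inflates RFS. Step 2 shows that it does not when withdrawal is non-informative.

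A third inference is that perioperative deaths would generally be lost. The preoperative CT probably means that most such patients have already been re-evaluated. Section 2.6 supports a small effect: of 14 Cohort A patients who reached the point of surgery, 3 were unresected, 2 for progression and 1 for liver toxicity from prior chemotherapy. Neither death nor withdrawal is given as a reason. However, 0/14 has a one-sided 95% upper bound of 1 - 0.05^(1/14) = 19%, and those patients do not inform Cohorts B and C.

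The measurable-disease part of the rule should remove few or no eligible patients, since section 3.1 already says "Patients must have measurable disease, defined as at least one lesion that can be accurately measured".

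Finally, RFS is secondary and section 13.4 plans no formal hypothesis test. That limits the importance of the point but does not settle which patients are analysed.

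**Conclusion.** The conflict is in the current text: 11.1.1 restricts recurrence evaluability to re-evaluated patients, against all enrolled subjects in 1.2 and death from any cause in 13.1. The upward bias arises only if 11.1.1 is applied to RFS and at least one patient dies before re-evaluation. It is then about 1.5 points per single death at n = 25 and 2.6 at n = 15, from an assumed 36.2%; with no such death it is zero. Neither the rate nor the number of early deaths comes from this trial, and the effect is probably small if the preoperative CT counts as re-evaluation. The documents do not support a claim that early deaths are in fact excluded, or that withdrawals add to the bias.

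The second RFS definition, in 11.1.5, has to be settled at the same time. Its treatment of unresected patients could move the estimate further (36.2% against 29.0% in the illustration) than one or two early deaths. The primary feasibility and safety conclusions are not affected.

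**What to change.** - **Section 11.1.1:** remove the re-evaluation condition for RFS and keep it only for tabulating preoperative tumour measurements.
- **Sections 11.1.5 and 13.1:** reconcile them so that there is one RFS time origin and one event definition, and death is included.
- **Section 13.4:** state that RFS and OS use all enrolled patients who received a neoadjuvant dose; that deaths before re-evaluation are events; that patients alive with no post-baseline assessment are censored at study entry for RFS; and how unresected patients are counted. Censoring at a last disease-free assessment would not work before resection, because patients must have measurable disease at entry.
- **Section 1.2:** align the wording with that set. Section 2.6 counts 2 screen failures among 18 enrolled, so all enrolled, taken literally, includes patients who were never treated.

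The cost is a few sentences and no new data collection. The RFS estimate may come out slightly less favourable.
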